Economic Evaluation Supplement Aim: To understand the economic impact of the Southwest Hub interventions. We hypothesize that both the NH and ER interventions' reduction in participant suicidal ideation and improved resilience will reduce participant healthcare and other community and personal costs compared to the standard of care of CM alone.

1. Administer a time use survey (e.g. time-logs) and conduct in-person interviews among the project staff and health workers. Using these tools, we will ask staff to recall how they allocated their time and what resources (e.g. supplies, equipment, etc.) they used.
2. Analyze Celebrating Life Apache surveillance system (CL) data for related data points for study participants, including intake and follow-up case management visits. This data counts the number of times study staff visited or attempted to visit study participants, and is key in accounting for the time and financial costs of conducting study visits with participants.

Diversity Supplement Aim: To assess individual characteristics (age, gender, substance use history, mental health status, educational and employment status, family composition) associated with co-occurrence of suicide ideation or attempts and history of opioid use compared with suicide risks alone

Secondary Aims:

2. To examine mediators and moderators of treatment effectiveness and sequencing in order to determine which types and sequence of interventions is best suited for which youth.
3. To assess the acceptability, feasibility and capacity for sustainability of the Hub's key intervention components (Surveillance/Case Management, New Hope and Elders' Resilience) from the perspective of multiple stakeholders as they are implemented across different tribes. This will also include identifying, prioritizing and testing strategies aimed at enhancing the sustainability of tribally implemented suicide prevention programs.

Opioid Data Collection Sub-Study Aim: Explore community beliefs about: a) correlates of risk (i.e., other substance use, mental health status, family, demographic and social factors), b) protective factors (cultural and spiritual factors) and c) behavior functions (i.e., emotional regulation, reinforcement patterns) of opioid abuse in Native American youth through focus groups with the existing Community Advisory Boards from the Hub partners.

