For the economic evaluation supplement, we will use all healthcare claims data for each intervention participant (from one year prior to the study period to 12 months post-enrollment--for a total of 2 years of participant claims data) requested from the Indian health Service's electronic health records to assess healthcare expenditures. We will also ask participants about their school performance and work attendance, as well as, some additional items related to time spent participating in the interventions. These new items for participants are included in the assessment battery.

As part of the economic evaluation supplement, we will collect data from staff about their time use and resources use. For this aim, we will ask all project case managers and health providers to collect daily time-logs. The design of the time-log may vary overtime to better fit program needs or activities. But in general, this tool will ask staff to select which of a pre-defined list of activities they conducted each day and for how many hours each activity. In-person interviews with staff will follow a semi-structure design. A survey tool will be used to guide open ended questions and the survey will be modified over-time to fit program activities.

We will also analyze CL data for related data points for study participants, including intake and follow-up case management visits. This data counts the number of times study staff visited or attempted to visit study participants, and is key in accounting for the time and financial costs of conducting study visits with participants.

For the diversity supplement, we will compare individual characteristics associated with co-occurrence of suicide ideation or attempts and opioid use vs. suicide ideation/attempt without concurrent opioid use risk. We will use

baseline measures of age, gender, mental health status, education, employment, academic status, income, and family composition already being collected by the parent grant.

Aim 2: To examine mediators and moderators of treatment effectiveness and sequencing in order to determine which types and sequence of interventions is best suited for which youth.

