Aim 1: We will randomize **304 participants**; 76 to CM alone, 76 to CM+NH, 76 to CM+ ER, and 76 to CM+NH+ER. Based on the previous work with the SIQ, we believe a 25% reduction among individuals with a score of 30 or greater would represent clinically significant change in suicide ideation.[5] Using pilot data of NH among the WMAT, an average baseline score of 45 could be expected on the SIQ.[5] A clinically significant reduction translates into a large Cohen's D effect size (>0.8). However, we want the power to observe the more moderate effect expected to result from comparing the sequencing of the interventions (NH+ER vs. NH+CM vs. CM+ER vs. CM alone). Using an adjusted alpha to account for multiple comparisons of 0.013, and a correlation of 0.2 among repeated measures, with four groups (NH+ER vs. NH+CM vs. CM+ER vs. CM alone), $n=58$ people per group ($n=116$ randomized at each randomization time-point) would provide 80% power to detect a small to moderate effect (Cohen's $F=0.2$). Adjusting these estimates for 30% attrition would result in $n=76$ per each of the four groups ($n=152$ per arm) for a total sample size of $N=304$.

Please note for our ***the Opioid Data Collection Sub-Study***: We will use a mixed methods approach to examine opioid use among our SMART trial participants through addition of a quantitative opioid related measure and qualitative interviews ($N=30$) with a subset of those who endorse recent or current use.

For the economic evaluation supplement: We will use the same sample of participants as Aim 1. We are not drawing statistical inferences about cost estimates so there is no sample size requirement. Instead, we are reporting on the health care services utilization and costs incurred by study participants before, during and after the intervention. To administer a time use survey and conduct in-person interviews we will use all HUB program case managers (five or more) and healthcare providers (three or more).

For the diversity supplement: We will use a sub-sample of $n=239$ WMAT participants enrolled in the parent trial. This sample size is based on the estimated enrollment rates during the Diversity Supplement study period.

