Intervention 1: New Hope is based on a brief empirically-validated Emergency Department (ED) intervention.[14-17] Our intervention, adapted with strong guidance from a Community Advisory Board (CAB), was designed to be implemented over 1 visit (2-4 hours) in a youth-preferred setting after ED discharge for a suicide attempt, and in the past few years has been updated to also target suicide ideation and binge behavior, including substance use more generally which could encompass opioids. Note: the intervention does not however focus directly on opioid use. NH emphasizes the seriousness of a suicide attempt; teaches coping skills to reduce risk, including emotion regulation, cognitive restructuring, social support, and safety planning; and helps participants overcome barriers to treatment motivation, initiation, and adherence. A center-piece of the intervention is a 20-minute video produced by WMAT-CAIH with Native actors, vignettes specific to this community, and Elders speaking in Apache (with sub-titles) about the seriousness of suicide, its impact on the community, their concern for the adolescent, and beliefs about the communal importance of each individual's life. **Youth are encouraged to choose a support person from his/her family to take part in the intervention because surveillance data indicated family conflict was one of the major reasons reported for suicide events and family members can reinforce skills including the youth's safety plan.**[17-19] The oral consent script for family members participating in New Hope will be used to introduce the intervention to the family member. NH is psychoeducation to supplement and promote mental health services, while encouraging connections to traditional healers and caring adults.[5] NH will be provided by CMHWs (and not Research Program Assistants) to reduce potential bias in the assessments. Intervention sessions will be recorded for quality assurance purposes. Two trained raters will use a standardized form to rate various components of the intervention session including—if all components of the lesson were delivered, the quality of delivery and the relationship between facilitator and participant.

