All youth will complete another study assessment after 30 days (**CM2**). The 30-day time frame will allow ample time to complete the NH intervention with participants and assess any changes in youth's mental health status for all study arms. Following another 30-day period (**CM3**), all participants will be re-assessed and re-randomized, using the same blocking and 1:1 ratio to either the Elders' Resilience (ER) intervention plus CM, or CM alone.

Randomization Procedure 2. Participants will be stratified by age groups (10-14, 15-19, and 20-29) and event type (ideation, attempt, binge + recent ideation), then randomized to intervention condition using a 1:1 assignment ratio.

Intervention 2: Elders' Resiliency (ER) intervention. Our CAB, Elder's Council and other key stakeholders have taught us that Apache traditions confer behavioral repertoires and values taught through storytelling, observation, and parenting at the family and community level that have carried the Apache people through generations of adversity and historical trauma. Starting in 2015, CAIH and local suicide prevention staff helped Apache Elders to create and teach a monthly manualized curriculum intended to bolster Apache youths' resilience to suicide ideation, attempts and substance abuse by promoting Apache cultural identity and values, youth's self-worth and role in the community, and fostering connectedness to society and community, *with an emphasis on extended family as a nexus of strength*. Each lesson

introduces youth to cultural knowledge, stories, and songs with an emphasis on respect and the sacredness of each life. Specific themes include: respect, Apache culture, spirituality, self-worth, endurance, gender roles, Apache history, education/work, responsibilities, relationships (including the clan system), discipline and communication. The Elders, CAIH, and suicide prevention team are now adapting the monthly curriculum into a brief intervention for youth who come through the surveillance system. ER will be provided by a separate CMHW and an Elder to reduce potential bias in the assessments.

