The current cadre of Elders teaching the school-based curriculum will be group from which we will select Elders for the study. For this study, our community-based Apache staff will select Elders who both express an interest in the current project and have demonstrated affinity and skill for teaching the current curriculum in the schools. After this group of Elders is recruited and agree to participate, they will be paired with our paraprofessional Apache study staff. This paring will be based on two primary factors: 1) previous experience working together, 2) not having a familial relationship. To avoid any conflicts that may arise, we will incorporate a process into our study policies and procedures manual and include it as part of the training for the Elders and Apache paraprofessionals. “If you have a concern or complaint with your co-teacher, please report them to our local PD, [name]. She will gather information from both individuals, facilitate a meeting to resolve any conflict, make a change in partners if necessary, and document the resolution (which may include a re-pairing).” In addition, our Elders will be trained on the following components: 1) the overall study protocol and accompanying policies and procedures manual, 2) the content and delivery of the Elders brief curriculum, 3) human subjects research, 4) Good Clinical Practice, and 5) our safety protocol that the accompanying case managers will complete at each visit (Elders will not be expected to implement/carry out the safety protocol). Intervention sessions will be recorded for quality assurance purposes. Two trained raters will use a standardized form to rate various components of the intervention session including—if all components of the lesson were delivered, the quality of delivery and the relationship between facilitator, Elder and participant.

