For the economic evaluation supplement aim: To evaluate healthcare expenditures per participant and intervention we will employ standard two-part regression models used in the analysis of healthcare costs. Variables per claim will include non-identifiable individual study ID, utilization date, charge per claim, and CPT code. Service claims will include all inpatient services and respective length of stay, ED services, outpatient services, specialist care, pharmaceuticals, home health, health transportation, and mental health care utilization and any other health-care related costs. In addition, time use of our staff will be categorized according to the various protocols that they work on. We will estimate the weekly total hours spent in delivering services to youth. The cost of the time allocated to youth services will be estimated by multiplying wage rate for that worker times hours spent delivering services to youth.

We will analyze Celebrating Life Apache surveillance system (CL) data for related data points for study participants, including intake and follow-up case management visits. This data counts the number of times study staff visited or attempted to visit study participants, and is key in accounting for the time and financial costs of conducting study visits with participants.

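### The costing plan makes no provision for the Elder who co-delivers Elders' Resilience (ER), so as written the delivery cost of ER and NH+ER would omit Elder time

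*Combined protocol and SAP*

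**What the plan says.** **Purpose.** Section I hypothesises lower costs with NH and ER than with CM alone. Section II sets out to report savings per participant for NH, ER and the two combined, and says the logs and interviews should account for everything needed to run the programs.

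**Who supplies the data.** Section III.A: "we will ask all project case managers and health providers to collect daily time-logs". Section III.B, covering both the time-use survey and the interviews: "we will use all HUB program case managers (five or more) and healthcare providers (three or more"). Section V.C.2 again directs the resource interviews to case managers and health providers. The aim in section I is worded more broadly: "conduct in-person interviews among the project staff and health workers".

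**How labour is costed.** Section V.C.4: "multiplying wage rate for that worker times hours spent delivering services to youth".

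**Who delivers the interventions.** Section V.C.1 on New Hope: "NH will be provided by CMHWs (and not Research Program Assistants) to reduce potential bias in the assessments". On Elders' Resilience: "ER will be provided by a separate CMHW and an Elder to reduce potential bias in the assessments". Elders are chosen from those already teaching the school curriculum, and "they will be paired with our paraprofessional Apache study staff". Section X.A.3 gives them a one-day group training. No section states an Elder wage or stipend, a source for Elder hours, or a rule for valuing them.

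**The concern.** The plan states a list of respondents and a costing rule. Applied literally, the two record no Elder hours. An Elder attends in person only in ER (in NH, Elders appear only on video), so an omission would fall on ER and NH+ER and leave NH and CM alone untouched. The error would therefore run in one direction, making the ER sequences look cheaper to deliver than they are.

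The figures are descriptive, but they are meant to be used. Section II says the tribe wants cost information for policy and for taking the programs to other tribal settings. A community budgeting from an ER cost without Elder time would be short of one of the two people who deliver each session.

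**Working it through.** The plan states no ER delivery cost, wage or Elder hours, so there is no figure to reproduce. The check has a textual part and an illustrative calculation.

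**1. Is the Elder within the costing sample?**

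- The operational lists (III.A, III.B, V.C.2) name case managers and health or healthcare providers.
- CMHWs are not named in them either, but they fit the health workers of the section I aim. Section V.C.1 also describes the Elder's companion as a case manager: "our safety protocol that the accompanying case managers will complete at each visit".
- Elders fit neither label clearly. Section V.C.1 recruits them separately and then pairs them with study staff, which places them outside staff.

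On this reading the CMHW's half of an ER session is logged and the Elder's half is not.

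**2. Session length.** Section V.C.2 gives CM visits of 2+1+1+1+1 = 6 h and 2-4 h for each intervention. A participant receiving both has 6 + 2×2 = 10 h to 6 + 2×4 = 14 h. Section VII.D states 6 h and 10-14 h, so the session length is consistent.

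**3. Elder in-session hours.** Section III.B assigns 76 to CM+ER and 76 to CM+NH+ER, so 76 + 76 = 152 are assigned to ER. Assume one session each, with one Elder present throughout.

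- All 152 receive it: 152×2 = 304 h to 152×4 = 608 h.
- Lower case of 116 recipients (2×58, the per-group number the power calculation asks for): 116×2 = 232 h to 116×4 = 464 h.

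Preparation, travel and the one-day training come on top. They cannot be computed, because neither the hours nor the number of Elders is given.

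**4. Share of labour cost omitted.** Let r be the Elder's hourly rate divided by the CMHW's. The documents do not give r, so it is an assumption. With one CMHW and one Elder present for the same time, leaving out the Elder omits r/(1+r) of ER in-session labour cost. For NH+ER, with equal session lengths and one CMHW in each session, it omits r/(2+r).

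| r (assumed) | ER: r/(1+r) | NH+ER: r/(2+r) |
|---|---|---|
| 0 | 0% | 0% |
| 0.25 | 20% | 11% |
| 0.5 | 33% | 20% |
| 1 | 50% | 33% |
| 2 | 67% | 50% |

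The Elder always supplies half of the in-session person-hours. Half of the labour cost follows only at r = 1.

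**The case against.** A reader might infer that Elders are left uncosted and that ER's cost is understated. The documents do not support that. No section excludes Elder cost, and no ER cost is stated that could be shown to be too low. Four counter-arguments deserve an answer.

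- **Interviews are a second source.** They are to record the number and type of resources used, and both tools may be revised as activities change. An interviewed case manager could report that an Elder took part. That stands as a possibility, but nothing requires it. Section I illustrates resources with supplies and equipment, and section II assigns staff time to the logs.
- **Elder session hours can be derived.** The paired worker's log should contain the same session. That also stands for in-session time. No rule says to add a second person's hours, however, and that log would not show preparation, travel or training specific to the Elder.
- **The labels are loose.** Read strictly, the lists name no CMHWs either, so NH delivery would be missing as well and the gap would not be confined to ER. This is a fair caution: the one-sidedness depends on CMHWs being covered. The section I wording and the description of the Elder's companion as a case manager make that the better reading.
- **The stakes are limited.** This is a supplement aim, and section III.B draws no inference on costs. The participant-level expenditure models use claims, which Elder time does not touch. All of that stands. It bounds the importance of the point, but a descriptive cost can still be biased.

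**Conclusion.** The plan does not provide for the Elder in its costing. If the respondent list and the wage-times-hours rule are followed as written, the delivery cost of ER and NH+ER would omit Elder time and look low relative to NH and CM alone. At stake are 304-608 Elder hours in session if all 152 receive ER, or 232-464 if 116 do. The omitted share of ER in-session labour cost is about 20% to 50% for an assumed pay ratio of 0.25 to 1, and 0% to 67% for ratios of 0 to 2.

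This rests on one CMHW and one Elder per session, one session per participant, and CMHWs being within the time-log group. The direction is firm if Elder time is omitted and has a positive value. The size is not, because Elder pay is unknown. The point should be fixed because Elder preparation and travel are hard to recover later. It does not affect claims-based expenditure, the SIQ or the resilience scales.

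**What to change.** Amend sections III.A, III.B and V.C.4 to bring Elders into the costing sample.

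1. For each ER session, the accompanying worker records the Elder's delivery, preparation and travel hours on an added line of the existing log.
2. Add the one-day Elder training to the ER cost.
3. Value Elder hours at actual pay or stipend. If Elders are unpaid, use a shadow wage stated in advance.
4. For sessions already completed, derive in-session hours from the paired worker's log or, where they record it, from session forms. Do not rely on the audio: section VI.C.3 has the recordings destroyed once quality ratings are done.
5. Define case manager, health provider and project staff, so that it is explicit that the CMHWs delivering NH and ER are logged.

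The cost is one log line per ER session and a few sentences in the plan. The reported ER and NH+ER costs will be less favourable to the extent that Elder time would otherwise have been left out. No participant contact or outcome analysis changes.
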